10.6 Handling measures

10.6.1 Measures for handling adverse drug reactions

The symptoms, signs, or laboratory test results, onset time, duration, severity, handling measures, course of events, etc., should be documented in the medical records. The correlation with the study drug should be assessed, and the investigator should sign and date the record. According to the adverse drug reaction reporting system, report the adverse drug reactions to the hospital's ADR monitoring center. The hospital's ADR monitoring center will then report to the provincial and national ADR monitoring centers.

10.6.2 Measures for handling adverse events

When an adverse event is identified, the investigator should immediately address it and report to the department head, determine necessary diagnostic and treatment measures based on the patient's condition, and decide whether to suspend the clinical study observation. All adverse events should be thoroughly investigated, with detailed records of the handling process and outcomes until a satisfactory resolution or stabilization of the condition. If there are laboratory abnormalities, follow-up should continue until recovery to normal. The follow-up method can be chosen based on the severity of the adverse reactions, including options such as hospitalization, outpatient visits, home visits, phone calls, and communication.

10.6.3 Measures for handling serious adverse events

10.6.3.1 Reporting

Investigators should report to the department head and promptly inform relevant personnel in the center project team based on the nature of adverse events. In the case of holidays or nighttime incidents, the on-duty medical staff should immediately notify the on-call administrative staff at the hospital and inform the director of the office of the drug clinical trial institution. The office of the drug clinical trial institution should report to the hospital's medical ethics committee, the study sponsor (lead center), relevant hospital departments, and Shijiazhuang Yiling Pharmaceutical Co., Ltd. within 24 hours. In emergency situations, including serious events, especially fatal adverse reactions and other serious adverse events, the

fastest communication methods (including phone, fax, express delivery, email, etc.) should be used to report to the above-mentioned departments.

Unit	Contact Person	Tel.	Fax
Ethics Committee of XXXX Hospital	XXXX	XXXX	XXXX
Beijing Tiantan Hospital, Capital Medical University	[name]	[name]	[name]
Shijiazhuang Yiling Pharmaceutical Co., Ltd.	[name]	[name]	[name]

(In case of a serious adverse event, report to relevant authorities within 24 hours)

10.7 Abnormal laboratory results

The investigator should assess whether the abnormal laboratory results are clinically significant and provide possible explanations. Abnormal laboratory results caused by reported adverse events should be simultaneously documented as adverse events in the adverse event table. Abnormal laboratory test results with clinical significance meeting one or more of the following conditions should be recorded as an independent diagnosis on the adverse event page of the study medical records (excluding abnormal laboratory results caused by reported adverse events):

- Accompanied by clinical symptoms;
- Resulting in changes to the study medication;
- Requiring modifications to concomitant medication and/or other therapeutic measures.

11 Blinding and Randomization

11.1 Code blinding, and blind code preservation

The biostatistician not involved in the data management and statistical analysis of this study uses the central randomization system to generate random drug packaging numbers. The randomization parameters cannot be modified or viewed after the project has commenced.

Based on the assigned drug packaging number, the drug is encoded by statisticians not involved in this study. The blind codes used for encoding must be sealed and preserved thereafter.

11.2 Emergency unblinding

In case of a serious adverse event requiring emergency unblinding, the responsible investigator at the center will log in to the randomization system for emergency unblinding. If, during the unblinding process, there are limitations due to internet speed or other reasons, directly call the 24-hour hotline of Peking University Clinical Research Institute. The system administrator will then proceed with the emergency unblinding. This unblinding process only involves the individual subject, and the system will not disclose information about the group assignment of other subjects. If the case undergoes emergency unblinding, it will be treated as a dropout; however, if adverse reactions occur, it will be included in the adverse event analysis.

11.3 Unblinding regulations

This study is double-unblinded. After blind verification, data locking is performed. The Principal Investigator, medical statistician, data administrator, and sponsor's representative conduct the first unblinding. The groups corresponding to each random number are labeled as A and B, to facilitate statistical analysis of all the data. When the statistical analysis is concluded, and the summary report is completed, the second unblinding is conducted to reveal the exact group assignments of A and B.

11.4 Randomization

11.4.1 Randomization method

Method of centralized dynamic randomization, with each center competing for enrollment. The centralized randomization procedure will be performed using the Interactive Web-based Randomization System (IWRS) provided by Peking University Clinical Research Institute. The principal investigators at each study center will have their own unique login credentials, ensuring the security and integrity of the login system. After screening each eligible subject at all participating centers in this study, the investigator will log in to the randomization system with their accounts, input relevant information about the subject and obtain the drug packaging number for that subject. The investigators will administer the relevant drug based on the drug

packaging number. Subjects will be randomized into treatment and control groups based on stratification factors, which include:

- 1. Whether thrombolytic therapy has been administered: Yes, No
- 2. NIHSS Score: 4–7 points, 8–14 points, 15–22 points

The randomization method is the Pocock and Simon minimization algorithm. Patients must initiate the study treatment within 24–48 hours after randomization. This study employs non-repeated randomization.

12 Statistical Analysis

After the study protocol is finalized, statistical professionals will collaborate with the principal investigator to develop the statistical analysis plan. The statistical analysis software used is SAS® 9.2 software (Software installation point authorization code: 11202165). The sample size calculation software used is PASS 11.

12.1 Analysis population

The study population is divided into the following categories:

- Full Analysis Set (FAS): The set of subjects according to the Intention To Treat (ITT) principle. It refers to the dataset composed of all subjects who participated in the randomization process and underwent baseline assessments. For subjects for whom complete efficacy assessments are not observed, data truncation will be carried out following the Last Observation Carried Forward (LOCF) principle.
- Per-Protocol Set (PPS): It refers to the collection of cases that meet the inclusion criteria, do not meet the exclusion criteria, and complete the treatment regimen. This includes cases that adhere to the study protocol, exhibit good compliance, and complete the specified CRF entries for analysis (PP analysis).
- Safety Set (SS): It refers to the set of all randomized subjects who received the study drug and had at least one safety assessment after baseline.

The efficacy analysis will be conducted based on the FAS and the PPS. The analysis of all baseline demographic data will be conducted based on the FAS, and safety assessment will be performed on the SS.

12.2 Statistical analysis method

- All statistical tests will be two-sided, and a *P*-value ≤0.05 (two-sided) will be considered statistically significant for the tested differences. (Unless specifically stated otherwise)
- Descriptive analysis: For count data, describe with proportions. For measurement data,

- describe with mean, standard deviation, maximum, and minimum values. For non-normally distributed data, describe with median, 25th percentile, and 75th percentile.
- The comparison of general conditions between the two groups will be analyzed using appropriate methods based on the type of indicator. Inter-group comparisons of quantitative data will be performed using paired t-tests or Wilcoxon rank-sum tests. For categorical data, the chi-square test or exact probability method will be employed. For ordinal data, Wilcoxon rank-sum tests or CMH tests will be used.

12.2.1. Enrollment and study completion:

Summarize the number of enrollments and completions for each center and provide a list of dropouts. Different dataset sizes for each group, distribution of cases in each center, comparison of overall dropout rates, and a detailed list of reasons for termination. Describe the demographic characteristics of patients (age, height, weight, vital signs, etc.), medical history, and medication history. Compare age, height, and weight between the two groups to assess their comparability.

12.2.2. Compliance analysis:

- Medication compliance analysis: Compare whether patients in the two groups use the study drug on time and in the correct dosage, and whether they refrain from using prohibited drugs and foods according to the protocol.
- Concomitant medication analysis: Tally the number of patients in each group using concomitant medications and provide a detailed list.

12.2.3. Efficacy evaluation:

- Baseline: Describe the baseline characteristics of each efficacy indicator. Refer to general methods for inter-group comparisons.
- Primary efficacy endpoints:

Conduct both PP and FAS analyses concurrently. The primary time point for evaluating the proportion of patients with improved modified Rankin (mRS) scores ≤ 1 in terms of activities of daily living is at Day 90 (for the PP population) or at the time of premature discontinuation (for the FAS population). The primary indicator will be compared between the two groups using the CMH- χ^2 analysis method, controlling for center effects.

The primary indicator will be assessed using a superiority test, testing the following hypothesis:

$$H_0: \pi_{Test\ group} - \pi_{Control\ group} \le 0$$

$$H_1: \pi_{Test\ group} - \pi_{Control\ group} > 0$$

$$\alpha = 0.025 (One - sided)$$

If the H_0 is rejected at the significance α level, or if the lower limit of the 95% CI for the difference in retention rates between the two groups is greater than 0, it can be considered that the treatment group is superior to the control group.

Other secondary indicators will be compared using the same statistical method as the primary indicator.

12.2.4. Safety evaluation:

Describe the number and proportion of subjects with normal values before treatment and abnormal values after treatment for both the treatment group and the control group separately. Describe adverse events using the number of cases, the number of subjects, and the incidence rate. Conduct inter-group significance tests will be conducted on the incidence rate. Additionally, provide a detailed description of the specific manifestations, severity, and the relationship with the drug for all adverse events observed in each group. Provide a cross-tabular description of the changes in laboratory indicators before and after the treatment. Compare vital sign indicators before and after the treatment.

13 Data Management

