rtPA Recombinant tissue plasminogen activator SAE Serious adverse event SFDA National Medical Products Administration TIA Transient ischemic attack TC Total cholesterol TCD Transcranial Doppler TG Triglyceride	RBC	Red blood cell		
SAE Serious adverse event SFDA National Medical Products Administration TIA Transient ischemic attack TC Total cholesterol TCD Transcranial Doppler TG Triglyceride	RCT	Randomized controlled trial		
SFDA National Medical Products Administration TIA Transient ischemic attack TC Total cholesterol TCD Transcranial Doppler TG Triglyceride	rtPA	Recombinant tissue plasminogen activator		
TIA Transient ischemic attack TC Total cholesterol TCD Transcranial Doppler TG Triglyceride	SAE	Serious adverse event		
TC Total cholesterol TCD Transcranial Doppler TG Triglyceride	SFDA	National Medical Products Administration		
TCD Transcranial Doppler TG Triglyceride	TIA	Transient ischemic attack		
TG Triglyceride	TC	Total cholesterol		
	TCD	Transcranial Doppler		
t-PA Tissue plasminogen activator	TG	Triglyceride		
	t-PA	Tissue plasminogen activator		
WBC White blood cell	WBC	White blood cell		

Protocol Synopsis

	1. The primary efficacy outcome was measured the			
	proportion of patients with modified Rankin Scale (mRS)			
	score ≤1 at 90 days after randomization. Subgroup analyses			
	for the primary outcome were conducted, based on TOAST			
	classification, reperfusion treatment, baseline NIHSS score			
	(4-7, 8-14 and 15-22), and AIS onset time to randomization			
	$(\leq 24, 24-48 \text{ and } 48-72 \text{ hours}).$			
	2. The secondary efficacy outcomes measured the proportion			
	of patients recovered to NIHSS 0-1 or reduction by 4 points			
	or more at 90 days, the proportion of patients with 85 or			
	more Bathel Index (BI) score at 90 days, distribution of			
Objective(s)	scores on the mRS (ordinal shift analysis) at 90 days,			
	incidence of ischemic cerebrovascular disease (ischemic			
	stroke, transient ischemic attack) and incidence of new			
	combination clinical vascular events (ischemic stroke,			
	hemorrhagic stroke, transient ischemic attack, myocardial			
	infarction, vascular death).			
	3. The following safety outcomes were also systematically			
	recorded: The incidence of adverse events, serious adverse			
	events, 12-lead electrocardiogram, physical examination and			
	laboratory test values (blood routine, urine routine, serum			
	biochemistry, coagulation).			
	A randomized, double-blind, placebo-controlled, and			

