4.2. Number of cases, grouping and study centers

According to the China National Stroke Registry (CNSR), 39.59% of patients with NIHSS Page 7 of 76

score of 4–22 at admission had mRS \leq 1 at 3 months. Assuming a 40% proportion of patients with mRS \leq 1 at 90 days in the control group and a 47% proportion in the treatment group, with an equal ratio design, and utilizing PASS 2008 to calculate the required sample size, with α = 0.05 (two-sided test) and β = 0.2 (test power 80%), the calculated sample size for both the treatment and control groups is 787 cases. To account for potential dropouts in clinical studies, an additional 20% of the sample size is added. Therefore, a total of 1,968 patients are planned to be included in this study.

Patients will be allocated in a 1:1 ratio to the treatment group and the control group, and the study is planned to be conducted at 50 centers nationwide.

5. Study Population

Patients entering the study must meet all the inclusion criteria listed below and must not meet any of the exclusion criteria. In addition to the criteria listed below, any medical conditions or use of prohibited medications during the standard treatment that are considered contraindications will also be grounds for excluding patients from the study.

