5.2 Secondary effect index

1. Improvement of neurological deficits (ratio of NIHSS≤1 or improve 4 score or more);

Improvement of neurological deficits (ratio of NIHSS≤1 or improve 4 score or more): It is effective for NIHSS≤1 or reducing 4 points or more; compare the ratio of efficacy and inefficacy and the continuous change of NIHSS between treatment group and control group 90 days after random treatment;

2. Improvement of daily life ability (ratio of BI index ≥85);

Ratio of patients with BI index≥85: BI score≥85 indicates the patient with ability of independent living; compare the ratio of patient with ability of independent living and continuous change of BI between treatment group and control group at 90 days after random treatment;

3. Disability rate (ratio of mRS score \geq 3)

mRS≥3 indicates the patient without self-care ability; compare the disability rate between treatment group and control group at 90 days after random treatment;

4. Continuous change of mRS score

Compare change of mRS score at baseline, 7d, discharge day and 90d between treatment group and control group;

5. Incidence of ischemic cerebrovascular diseases during follow-up period;

Ratio of ischemic stroke or TIA within 90 days after random treatment, or ratio of new ischemic focus detected by MRI during the last visit, and take this kind of patients as a group for evaluation or respective evaluation:

6. Incidence of combined vascular events during follow-up period;

Accumulated ratio of patients having newly combined vascular events within 90 days after random treatment;

Definition of combined vascular events: Include any type of stroke (ischemic stroke and hemorrhagic stroke), TIA, myocardial infarction and vascular death.

Vascular death: Hemorrhagic death or fatal pulmonary embolism of any organ.

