6.2 Statistical method

6.2.1 General principle

SAS9.4 software is adopted for statistical analysis. All data are performed with two-sided test, and P value less than or equal to 0.05 (two-sided test) is considered with statistical difference. (Unless the special instruction)

Quantitative indexes are described with case number, mean, standard deviation, median, P25 (Q1), P75(Q3), minimum value (Min) and maximum value (Max).

Classification indexes are described with case number and percentage.

Comparison of general situation should be analyzed with appropriate method based on the type of indexes. Quantitative data should be analyzed with paired t test or Wilcoxon rank sum test; classification data with chi-square test or precise probability method, and ranked data with Wilcoxon rank-sum test or CMH test.

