6.2.4 Efficiency evaluation

Baseline efficiency: Describe the baseline of each curative index, and comparison between groups should be made in accordance with general condition. Modified Rankin (mRS) score is regarded as ranked data, and should be compared with Wilcoxon rank sum test. NIHSS score should be regarded as quantitative data and ranked data (4-7 points, 8-14 points and 15-22 points) for description and comparison; BI score as quantitative data and enumeration data (<85 points, ≥85 points) for description and comparison.

Primary efficiency indexes:

PP analysis and FAS analysis should be performed at the same time; evaluation on patients with modified Rankin (mRS) score≤1 should be mainly conducted ontaken at day 90 day (PP set) and the time for suspending and drop-out (FAS set). Primary indexes should be compared between the two groups with CMH-γ2 method for controlling central effect.

Superiority test is adopted for primary indexes, and the hypotheses under test are as follows:

$$H_0$$
: $\pi_{\text{treatment group}} - \pi_{\text{control group}} \le 0$

$$H_1: \pi_{\text{treatment group}} - \pi_{\text{control group}} > 0$$

$$\alpha = 0.025_{\text{(one-sided)}}$$

The treatment group is superior to control group, if H0 is rejected under α level, or lower limit of 95% Cl for difference of retention rate between the two groups is higher than 0. Take sensitivity analysis on primary efficiency indexes with modified Rankin (mRS) score≤2 points as the limit.

Other secondary indexes can be statistically analyzed in accordance with methods for primary indexes.

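### The between-group rule for quantitative data names a paired t-test although the arms are independent, score changes have no fitting named test, and the synopsis's Day-90 mRS shift endpoint has no ordinal estimate or distribution table.

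*Combined protocol and SAP*

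**What the plan says.** **Design.** Protocol section 4 describes a parallel-group trial. Section 11.4.1 and SAP 4.2 allocate patients individually by minimisation on thrombolysis and NIHSS category. Neither document defines matched pairs.

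**General rule.** Under the comparison of general patient characteristics, protocol 12.2 states: "Inter-group comparisons of quantitative data will be performed using paired t-tests or Wilcoxon rank-sum tests". SAP 6.2.1 has: "Quantitative data should be analyzed with paired t test or Wilcoxon rank sum test". For ordinal data both name the rank-sum or CMH test. Neither says how to choose between the options.

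**Secondary efficacy rule.** SAP 6.2.4: "Other secondary indexes can be statistically analyzed in accordance with methods for primary indexes". Protocol 12.2.3 says the same. The primary method is a CMH chi-square controlling for centre, with hypotheses written as a difference of two proportions.

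**mRS secondary endpoint.** The synopsis lists the distribution of "scores on the mRS (ordinal shift analysis) at 90 days". Protocol 7.1.2 and 9.1.2 list continuous change of mRS over the visits instead, and SAP 5.2 has: "Compare change of mRS score at baseline, 7d, discharge day and 90d between treatment group and control group". The SAP output is Table 7.3.6.1, which gives summary statistics for the score and its change, with unnamed test and P-value rows.

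**The concern.** A paired t-test needs a one-to-one link between a patient in one arm and a patient in the other. No such link exists here, and the two arms need not contribute equal numbers. The secondary scores are especially exposed, because SAP 6.1.1 analyses them on actual data without carry-forward and the sample size allows for 20% dropout. A programmer following the text would have to invent a pairing, change the test without authority, or default to rank-sum.

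The second gap is in efficacy. Change in NIHSS, BI and mRS is to be compared between arms, but the stated secondary method handles proportions and the shells leave the test blank. The third gap is that the synopsis promises a shift analysis of Day-90 mRS for which the SAP plans no model, effect measure or distribution table. A test or model picked after the A/B unblinding would not be prespecified, and the choice could be questioned.

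**Working it through.** **1. Where the paired t-test applies.** Reading each comparison against its governing text:

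| Comparison | Governing text | Test named |
|---|---|---|
| Demographics; baseline NIHSS and BI as quantitative data | 12.2 and SAP 6.2.1, also by reference from 12.2.3 and SAP 6.2.4 | Paired t or rank-sum |
| Vital signs, baseline and Day 90 | SAP 6.2.5, by reference to the general principles | Paired t or rank-sum |
| Baseline mRS | SAP 6.2.4, baseline paragraph | Rank-sum |
| Binary NIHSS, BI and disability endpoints | 12.2.3, SAP 6.2.4 | CMH on proportions (fits) |
| Change in NIHSS, BI and mRS | 12.2.3, SAP 6.2.4 | CMH on proportions (does not fit); shells unnamed |
| Day-90 mRS distribution (synopsis) | No counterpart in body or SAP | None |

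The paired t-test is therefore written for baseline and vital-sign comparisons. It reaches the score changes only if an analyst falls back on the general rule.

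**2. The plan's own sample size (protocol 4.2, SAP 4.4).** Inputs: control 0.40, treatment 0.47, two-sided α 0.05, power 80%, 1:1 allocation.

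n per arm = [z₀.₉₇₅·√(2·p̄·(1−p̄)) + z₀.₈·√(p₁(1−p₁)+p₂(1−p₂))]² / (p₂−p₁)², with p̄ = 0.435.

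- First term: 1.960 × √0.49155 = 1.374.
- Second term: 0.8416 × √0.4891 = 0.589.
- n = 3.852 / 0.0049 = 786.2, rounded up to 787.
- Dropout: 787 / 0.80 = 983.75, rounded up to 984 per arm, 1,968 in total.

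This matches the plan. It rests on the binary primary endpoint, so nothing in this point changes it.

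**3. Would a paired t-test on unmatched arms give wrong numbers?** The documents give no full mRS distribution, so three seven-level control distributions (0–6) were assumed, each with 40% at 0–1:

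- A: .15, .25, .18, .17, .14, .06, .05
- B: .10, .30, .20, .20, .12, .05, .03
- C: .20, .20, .12, .13, .15, .12, .08

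Treatment was a proportional-odds shift with OR = (0.47/0.53)/(0.40/0.60) = 1.33. There were 787 per arm and 3,000 runs per scenario (Monte Carlo standard error at 5%: √(0.05×0.95/3000) = 0.4 points).

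| Test | Type I error, A / B / C | Power, A / B / C |
|---|---|---|
| Paired t, arbitrary pairing | 5.0 / 5.2 / 5.4% | 87.5 / 87.1 / 88.5% |
| Two-sample t | 5.0 / 5.1 / 5.3% | 87.4 / 87.2 / 88.5% |
| Rank-sum | 4.8 / 5.4 / 5.2% | 88.7 / 88.7 / 89.0% |
| Paired t after sorting each arm by outcome | 84.0 / 84.0 / 86.2% | not meaningful |

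The critical values are almost equal: 1.963 (paired, 786 df) against 1.961 (two-sample, 1,572 df). Arbitrary pairing does not inflate error. Only pairing on the sorted outcome does, and nobody proposes that.

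**4. How far the result depends on the pairing.** With equal variances, paired t = two-sample t × (1−r)^(−1/2), where r is the chance correlation that the pairing creates. Its SD is 1/√786 = 0.036. At r = ±0.071 (2 SD) the factor runs from 0.966 to 1.038. A two-sample t of 1.961 becomes anything from 1.895 (P = 0.058) to 2.035 (P = 0.042), depending on patient order alone. Results far from the threshold hardly move.

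**5. The shift endpoint.** Table 7.3.6.1 has a Day-90 mRS row by arm with mean, SD, median, quartiles, range, an unnamed statistic and a P value. It has no count per mRS level and no ordinal effect measure. No other shell supplies either; Tables 7.3.2.1 and 7.3.2.2 dichotomise the score. Appendix 2 defines levels 0 to 5 only, so a patient who has died has no stated score.

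**The case against.** The strongest reply is that the word paired is a slip. The alternative beside it, rank-sum, is an independent-samples test. The shells for change carry two sets of statistics and P values, which would suit a within-arm paired test plus a between-arm test, and SAP 6.2.5 asks for both kinds of comparison for vital signs. That is plausible, but the text does not say it, so it supports a simple correction rather than leaving the rule alone.

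A reader might infer that all secondary score comparisons are specified as paired t-tests and that their results would be wrong. The documents do not support this. The rule sits under general characteristics, secondary endpoints have their own rule, a valid rank-sum test is always offered, and arbitrary pairing left type I error near 5%.

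A reader might also infer that mRS at Day 90 has no between-arm comparison, or only a comparison of mean change. That goes too far as well. The Day-90 row exists, with median and quartiles; both documents allow rank-sum or CMH for ordinal data; and SAP 6.2.4 treats mRS as ranked, though only at baseline. A rank-sum test in that row would be a recognised test of shift. What is missing is the named test, the effect estimate and the distribution.

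Finally, ANCOVA and proportional odds are choices among valid methods, and ANCOVA on NIHSS and BI itself treats score steps as equal. That stands: the correction required is a fitting, named method, and those offered below are reasonable candidates.

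**Conclusion.** The point holds in a limited form, as something that should be corrected. The paired option in protocol 12.2 and SAP 6.2.1 is undefined for independent arms and irreproducible, but it is not shown to be numerically biased. It directly affects baseline scores and vital signs. Changes in NIHSS, BI and mRS have a stated method that does not fit and shells without a named test. One synopsis secondary endpoint, the Day-90 mRS shift, has no ordinal effect estimate or distribution table. The primary endpoint, 787 per arm and 1,968 in total are untouched.

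The simulated error rates and powers rest on assumed mRS distributions, including a level 6 for death that Appendix 2 does not define, and are illustrative. The findings on scope and on the missing analyses rest on the text alone.

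**What to change.** 1. In protocol 12.2 and SAP 6.2.1, replace the paired t-test with a two-sample t-test for between-group comparisons. Keep paired tests only for before/after change within an arm.
2. Compare Day-90 NIHSS and BI by ANCOVA on the baseline score plus the minimisation factors (NIHSS category, thrombolysis), retaining centre, with rank-sum as the alternative if distributions are strongly skewed. Name the test in each shell.
3. Reconcile the mRS endpoint across the synopsis, protocol 7.1.2 and 9.1.2, and SAP 5.2. Add a Day-90 mRS distribution table with a named ordinal analysis: for example, a proportional-odds common odds ratio adjusted for the minimisation factors, or a stratified rank or CMH test. State how deaths are scored. Keep mean mRS change as descriptive.

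The cost is SAP wording, one table shell and a death-scoring rule, with no new data. The changes should be made before the first (A/B) unblinding.

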5.4. Termination criteria

- 1) Occurrence of allergic reactions clearly related to the study drug;
- 2) Occurrence of adverse symptoms, signs, or abnormal test results clearly related to the study drug, as judged by the investigator, necessitating the termination of the study;
- 3) Occurrence of pregnancy in females during the study period;
- 4) Termination of continued participation in the study at the patient's request;
- 5) Undergoing endovascular therapy during the study period;
- 6) The occurrence of vascular events will be evaluated on a case-by-case basis: In the event of hemorrhagic stroke, the study drug should be discontinued, the study terminated, and the details documented in the relevant sections of the study medical records. If a TIA/ischemic stroke/myocardial infarction occurs, the subject does not need to discontinue the study drug or withdraw from the study unless the use of concomitant medication contraindicated in this study is necessary.

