6.1.6.3 Handling plan for patients permanently discontinuing the drug

The follow-up of patients should adhere to the procedures specified in the study protocol, continuing until the scheduled completion date of the study or until the patient recovers to normal or stable condition from adverse events (whichever is longer).

The investigator should record all confirmed withdrawals from the study on the corresponding pages of the CRF.

Patients who discontinue the study drug before the last follow-up should complete the endpoint follow-up at 3 months.

For patients lost to follow-up, relevant information should be documented up to the last follow-up in their CRFs. The investigator should make every effort to contact each patient, ascertain the reason for loss to follow-up, and assess their health status.

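### Protocol and SAP place the main (FAS) evaluation of the primary endpoint at discontinuation or drop-out, which conflicts with the Day-90 endpoint, and no analysis tests the LOCF assumption

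*Combined protocol and SAP*

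**What the plan says.** The synopsis and protocol 9.1.1 define the primary outcome as the proportion with mRS ≤1 at 90 days after randomization.

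Protocol 12.2.3 sets the time point for evaluating it "at Day 90 (for the PP population) or at the time of premature discontinuation (for the FAS population"). SAP 6.2.4 has the same split: "at day 90 day (PP set) and the time for suspending and drop-out (FAS set"). SAP 6.1.1 names the FAS as the main population for efficacy.

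Other sections point to Day 90:

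- Protocol 6.1.6.3: "Patients who discontinue the study drug before the last follow-up should complete the endpoint follow-up at 3 months". Visit 4 (protocol 8.4) includes the mRS.
- Protocol 12.1 applies LOCF where complete efficacy assessments were not observed. SAP 6.1.1 applies it when the primary index is missing.
- SAP Table 7.3.2.1 reports 90-day mRS in its FAS columns, with a row for missing values.

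Several rules turn patients into drop-outs or terminations. Protocol 5.3 lists adverse events, lack of efficacy and endovascular therapy among the common reasons. Protocol 11.2 says of emergency unblinding: "If the case undergoes emergency unblinding, it will be treated as a dropout". Protocol 5.4 says: "In the event of hemorrhagic stroke, the study drug should be discontinued, the study terminated".

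The one sensitivity analysis for the primary outcome is in SAP 6.2.4: "Take sensitivity analysis on primary efficiency indexes with modified Rankin (mRS) score≤2 points as the limit".

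**The concern.** The two sections that define the primary analysis assign Day 90 only to the per-protocol set. For the main population they name a different, patient-specific time. No rule says which value prevails when a patient stops drug early and is then seen at Day 90, so two analysts could build two different primary datasets and each cite the plan.

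The timing matters because function is still changing over these 90 days. The scheduled mRS assessments before Visit 4 are baseline, Day 7 and discharge (Day 21 if the stay is longer). A carried-forward score therefore usually describes early recovery. The protocol FAS requires only randomization and a baseline assessment, so even a baseline mRS could be carried forward. The SAP FAS requires some post-treatment assessment. Some drop-out reasons are related to outcome, so drop-out need not be balanced between arms, and imbalance would bias the main result in either direction. Moving the cut-off to mRS ≤2 leaves the carried-forward scores in place and cannot reveal this.

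**Working it through.** **1. The plan's own figure.** Protocol 4.2 assumes 40% and 47%, two-sided α 0.05 and 80% power. With the pooled-variance formula and mean rate 0.435:

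n = [1.96·√(2·0.435·0.565) + 0.842·√(0.40·0.60 + 0.47·0.53)]² / 0.07² = 786.2, so 787 per arm.

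787/0.8 = 983.75, so 984 per arm and 1,968 in total. The plan reproduces.

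**2. The texts compared.** For a patient who stops drug on Day 10 and attends Day 90:

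- Protocol 12.2.3 and SAP 6.2.4, read literally, use the score at discontinuation.
- Protocol 9.1.1 and SAP Table 7.3.2.1 use the Day-90 score.
- The LOCF rules in protocol 12.1 and SAP 6.1.1 are not triggered, because the Day-90 score was observed.

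These cannot all be followed.

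**3. Size of a possible bias.** The following are assumptions, not in the documents: drop-out rates dT and dC of 10% and 15%, in either order; a carried-forward success rate q of 15–25%, equal in both arms; and drop-outs who would have reached the same Day-90 rates as completers. The 40%, 47% and 984 per arm are the plan's. The calculation is a simple two-proportion comparison without centre stratification.

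FAS rate in an arm = (1 − d)·p + d·q.

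*No true effect (p = 0.40 in both arms), dT = 10%, dC = 15%.* Spurious difference = (dC − dT)·(0.40 − q).

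- q = 0.15: 0.05 × 0.25 = 1.25 points (37.5% vs 36.25%). SE = √[(0.375·0.625 + 0.3625·0.6375)/984] = 0.0218. One-sided error = 1 − Φ(1.96 − 0.0125/0.0218) ≈ 8%.
- q = 0.25: 0.05 × 0.15 = 0.75 points (38.5% vs 37.75%). SE = 0.0219. One-sided error ≈ 5%.

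The nominal level is 2.5%.

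*True 7-point effect, dT = 15%, dC = 10%.*

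- q = 0.15: 0.85·0.47 + 0.15·0.15 = 42.2%; 0.90·0.40 + 0.10·0.15 = 37.5%; difference 4.7 points.
- q = 0.25: 43.7% vs 38.5%; difference 5.2 points.

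*True 7-point effect, dT = 10%, dC = 15%.* The difference is 7.55 points (q = 0.15) or 7.05 points (q = 0.25), because dilution and imbalance then act in opposite directions.

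**The case against.** The strongest defence is that the LOCF rules are conditional. If Day-90 mRS is observed it is not missing, Table 7.3.2.1 is labelled as 90-day mRS, and the wording of 12.2.3 and SAP 6.2.4 may be loose shorthand for Day 90 if available, otherwise the last value. This is a fair reading. It means the documents do not establish that collected Day-90 scores will be overwritten, only that the literal text allows it and nothing settles it. It does not answer the rest: on this reading LOCF is still the primary method and still untested.

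Three stronger readings are tempting, and the documents do not support them.

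- *Every drop-out will have a Day-90 score.* Protocol 6.1.6.3 asks for the 3-month follow-up after stopping drug, but for withdrawn patients protocol 5.3 asks for endpoint follow-up only where possible. Some scores will be truly missing.
- *After a haemorrhagic stroke or other terminating event, a score from before the event stands as the outcome.* Protocol 8.6 calls for an mRS within the 72-hour documentation of new neurological symptoms, and 5.3 asks for a final assessment at withdrawal. A post-event score is planned, though it is not a Day-90 score.
- *LOCF costs the trial its 80% power.* With 20% drop-out, q of 15–25% and no effect in carried-forward scores, the difference is 0.8 × 7 = 5.6 points and power at 984 per arm is 72–73%. If those scores hold half the effect, power is 81–82%. Even with no effect in them, it stays at 80% or more when drop-out is below about 11%. Collecting Day-90 mRS on everyone gives 70.9% if the 20% who discontinue have no effect, and 88.0% if they keep all of it. The loss comes from assuming no effect in discontinuers, not from LOCF itself.

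**Conclusion.** The contradiction stands on the text of both documents, and it concerns the primary outcome variable in the main population, so it should be settled before unblinding. Followed literally, 12.2.3 and SAP 6.2.4 do not estimate the Day-90 endpoint for patients who discontinue. Followed kindly, the main result rests on an LOCF assumption that no planned analysis tests.

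Under the assumed inputs, imbalance of 5 percentage points in drop-out creates a spurious 0.75–1.25 points and a one-sided error of about 5–8%, or reduces a true 7 points to 4.7–5.2. These figures illustrate sensitivity and are not predictions. Under no effect, the bias vanishes if drop-out is balanced or if carried-forward success equals the Day-90 rate. No conclusion about lost power is drawn.

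**What to change.** In protocol 12.2.3 and SAP 6.1.1 and 6.2.4:

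1. State that the FAS primary analysis uses the observed Day-90 (±7 days) mRS regardless of drug discontinuation, emergency unblinding, endovascular therapy or vascular event.
2. State that classification as a drop-out or termination under protocol 5.3, 5.4 or 11.2 does not end Day-90 outcome collection unless consent is withdrawn. This concerns outcome collection only and leaves the treatment-stopping rules unchanged.
3. For a truly missing Day-90 mRS, specify a method using the collected Day-7 and discharge scores and baseline covariates. Multiple imputation is one acceptable choice. Keep LOCF at most as a sensitivity analysis.
4. Count deaths as failures. Appendix 2 lists mRS levels 0 to 5 only, so a death rule has to be written.
5. Add a missing-equals-failure or tipping-point sensitivity analysis.
6. Reconcile the FAS time point with protocol 6.1.6.3 and 9.1.1 and SAP Table 7.3.2.1.

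The cost is wording and modest programming. No visit is added to the schedule, although reaching withdrawn patients at Day 90 will take more effort than the present best-efforts wording implies. The change aligns the main analysis with the stated endpoint but does not guarantee 80% power.
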